6.2 Treatment of Nivolumab or Ipilimumab Related Infusion Reactions

Since nivolumab and ipilimumab contain only human immunoglobulin protein sequences, it is unlikely to be immunogenic and induce infusion or hypersensitivity reactions. However, if such a reaction were to occur, it might manifest with fever, chills, rigors, headache, rash, pruritis, arthralgias, hypo- or hypertension, bronchospasm, or other symptoms.

All Grade 3 or 4 infusion reactions should be reported as an SAE if criteria are met. Infusion reactions should be graded according to NCI CTCAE v4.03 guidelines.

Treatment recommendations are provided below and may be modified based on local treatment standards and guidelines as appropriate:

- Grade 1 symptoms: (Mild reaction; infusion interruption not indicated; intervention not indicated). Remain at bedside and monitor subject until recovery from symptoms. The following prophylactic premedications are recommended for future infusions:
 - Diphenhydramine 50 mg (or equivalent) and/or paracetamol 325 to 1000 mg (acetaminophen) at least 30 minutes before additional nivolumab administrations.
- Grade 2 symptoms: (Moderate reaction requires therapy or infusion interruption but responds promptly to symptomatic treatment [eg, antihistamines, non-steroidal anti-inflammatory drugs, narcotics, corticosteroids, bronchodilators, IV fluids]; prophylactic

medications indicated for 24 hours). Stop the nivolumab or ipilimumab infusion, begin an IV infusion of normal saline, and treat the subject with diphenhydramine 50 mg IV (or equivalent) and/or paracetamol 325 to 1000 mg (acetaminophen); remain at bedside and monitor subject until resolution of symptoms. Corticosteroid or bronchodilator therapy may also be administered as appropriate. If the infusion is interrupted, then restart the infusion at 50% of the original infusion rate when symptoms resolve; if no further complications ensue after 30 minutes, the rate may be increased to 100% of the original infusion rate. Monitor subject closely. If symptoms recur, then no further nivolumab or ipilimumab will be administered at that visit. Administer diphenhydramine 50 mg IV, and remain at bedside and monitor the subject until resolution of symptoms. The amount of study drug infused must be recorded on the electronic case report form (eCRF). The following prophylactic pre-medications are recommended for future infusions:

- Diphenhydramine 50 mg (or equivalent) and/or paracetamol 325 to 1000 mg (acetaminophen) should be administered at least 30 minutes before additional nivolumab or ipilimumab administrations. If necessary, corticosteroids (recommended dose: up to 25 mg of IV hydrocortisone or equivalent) may be used.
- Grade 3 or Grade 4 symptoms: (Severe reaction, Grade 3: prolonged [ie, not rapidly responsive to symptomatic medication and/or brief interruption of infusion]; recurrence of symptoms following initial improvement; hospitalization indicated for other clinical sequelae [eg, renal impairment, pulmonary infiltrates]). Grade 4: (life threatening; pressor or ventilatory support indicated). Immediately discontinue infusion of nivolumab or ipilimumab. Begin an IV infusion of normal saline, and treat the subject as follows. Recommend bronchodilators, epinephrine 0.2 to 1 mg of a 1:1,000 solution for subcutaneous administration or 0.1 to 0.25 mg of a 1:10,000 solution injected slowly for IV administration, and/or diphenhydramine 50 mg IV with methylprednisolone 100 mg IV (or equivalent), as needed. Subject should be monitored until the investigator is comfortable that the symptoms will not recur. ***Nivolumab or ipilimumab will be permanently discontinued.*** Site investigators should follow their institutional guidelines for the treatment of anaphylaxis. Remain at bedside and monitor subject until recovery from symptoms. In the case of late-occurring hypersensitivity symptoms (eg, appearance of a localized or generalized pruritis within 1 week after treatment), symptomatic treatment may be given (eg, oral antihistamine, or corticosteroids).

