6.1.2 Criteria to Resume Treatment

Subjects may resume treatment with study drugs when the drug-related AE(s) resolve to Grade ≤ 1 or baseline value, with the following exceptions:

- Subjects may resume treatment in the presence of Grade 2 fatigue
- Subjects who have not experienced a Grade 3 drug-related skin AE may resume treatment in the presence of Grade 2 skin toxicity

- Subjects with baseline Grade 1 AST/ALT or total bilirubin who require dose delays for reasons other than a 2-grade shift in AST/ALT or total bilirubin may resume treatment in the presence of Grade 2 AST/ALT OR total bilirubin
- Subjects with combined Grade 2 AST/ALT AND total bilirubin values meeting discontinuation parameters (Section 6.3.3) should have treatment permanently discontinued
- Drug-related pulmonary toxicity, diarrhea, or colitis, must have resolved to baseline before treatment is resumed
- Drug-related endocrinopathies adequately controlled with only physiologic hormone replacement may resume treatment

If the criteria to resume treatment are met, the subject should restart treatment at the next scheduled timepoint per protocol (i.e., missed doses are NOT made up).

If treatment is delayed > 6 weeks, (from the first missed dose) the subject should be permanently discontinued from study therapy, except as specified in discontinuation section below.

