6.1.3 Discontinuation Criteria

Treatment should be permanently discontinued for the following:

- Any Grade 2 drug-related uveitis or eye pain or blurred vision that does not respond to topical therapy and does not improve to Grade 1 severity within the re-treatment period OR requires systemic treatment
- Any Grade 3 non-skin, drug-related adverse event lasting > 7 days, with the following exceptions for drug-related laboratory abnormalities, uveitis, pneumonitis, bronchospasm, diarrhea, colitis, neurologic adverse event, hypersensitivity reactions, and infusion reactions
 - Grade 3 drug-related uveitis, pneumonitis, bronchospasm, diarrhea, colitis, neurologic adverse event, hypersensitivity reaction, or infusion reaction of any duration requires discontinuation (**NOTE:** Subjects with Grade 3 diarrhea or colitis while on Part B ipilimumab/nivolumab combination therapy could resume nivolumab alone if toxicity resolves to at least Grade 1 off of immunosuppressive drugs by end of week 16. Nivolumab monotherapy cannot start until toxicity is resolved to at least Grade 1 off immunosuppression x 2 weeks and cannot begin before week 13 or after week 19.
- Grade 3 drug-related laboratory abnormalities do not require permanent treatment discontinuation except those noted below
 - Grade 3 drug-related thrombocytopenia > 7 days or associated with bleeding
 - Any drug-related liver function test (LFT) abnormality that meets the following criteria require discontinuation:
 - AST or ALT > 8 x ULN
 - Total bilirubin > 5 x ULN
 - Concurrent AST or ALT > 3 x ULN and total bilirubin > 2 x ULN

- Any Grade 4 drug-related adverse event or laboratory abnormality, except for the following events which do not require discontinuation:
 - Isolated Grade 4 amylase or lipase abnormalities that are not associated with symptoms or clinical manifestations of pancreatitis and:
 - Decrease to < Grade 4 within 2 weeks of onset in the absence of immunosuppressive therapy.
 - Decrease to < Grade 4 and maintain < Grade 4 for a minimum of 1 week after stopping immunosuppressive therapy.
 - Isolated Grade 4 electrolyte imbalances/abnormalities that are not associated with clinical sequelae and are corrected with supplementation/appropriate management within 72 hours of their onset
- Any dosing interruption lasting > 6 weeks (from scheduled dose) with the following exceptions:

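### The Grade 2 infusion-reaction instructions allow re-dosing after symptoms recur on restart, an event the protocol elsewhere grades 3 and answers with permanent discontinuation

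*Combined protocol and SAP*

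**What the plan says.** Four pieces of text bear on a reaction that recurs after the infusion is restarted. Two sections carry the number 6.2; the one meant here is Treatment of Nivolumab or Ipilimumab Related Infusion Reactions.

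- **Section 6.2, Grade 2 bullet.** Stop the infusion and treat. Then: "If the infusion is interrupted, then restart the infusion at 50% of the original infusion rate when symptoms resolve". On recurrence: "If symptoms recur, then no further nivolumab or ipilimumab will be administered at that visit". Diphenhydramine and bedside monitoring follow. The bullet then recommends premedication for later infusions, which "should be administered at least 30 minutes before additional nivolumab or ipilimumab administrations".
- **Section 6.2, Grade 3 or 4 bullet.** The Grade 3 descriptor includes "recurrence of symptoms following initial improvement; hospitalization indicated for other clinical sequelae". The action is: "Nivolumab or ipilimumab will be permanently discontinued".
- **Section 6.1.3, Discontinuation Criteria.** Among the Grade 3 drug-related events that end treatment, a "hypersensitivity reaction, or infusion reaction of any duration requires discontinuation".
- **Section 6.1.2, Criteria to Resume Treatment.** Once a drug-related event has resolved to Grade 1 or less, or to baseline, "the subject should restart treatment at the next scheduled timepoint per protocol".

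Section 6.2 also says that infusion reactions are graded by CTCAE v4.03, and that its treatment advice may be adapted to local standards.

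**The concern.** The Grade 2 bullet deals with recurrence explicitly and appears complete: give no more drug at this visit, treat, observe, premedicate next time. It does not tell the site to regrade the event and does not point to Section 6.1.3. Limiting the stop to the current visit implies that there will be another dose. Yet the event described meets the protocol's own Grade 3 wording, for which the stop is permanent.

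The main stake is patient safety, namely re-exposure of someone who should have come off treatment. The grade assigned also affects three other things:

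- **Acute care.** Epinephrine is named only in the Grade 3 or 4 bullet.
- **Reporting.** Section 6.2 ties consideration as an SAE to Grade 3 and 4 infusion reactions.
- **Part B entry.** Section 5.2 (Part B: Nivolumab + Ipilimumab) excludes patients with Grade 3 non-endocrine toxicity on monotherapy. A Part A recurrence left at Grade 2 would not trigger that exclusion.

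**Working it through.** The plan gives no figure to reproduce. The check is to follow one patient through the text and then to work out when re-dosing would occur.

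**Trace of the event**

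1. A Grade 2 reaction occurs. The infusion is stopped and the patient is treated.
2. The infusion is restarted at 50% of the original rate, but only after symptoms have resolved. Improvement has therefore already occurred.
3. Symptoms return, so the recurrence necessarily follows improvement.
4. From here the text gives two outcomes:

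| Route | Text applied | Outcome |
|---|---|---|
| Stay in the Grade 2 bullet | 6.2 Grade 2, then 6.1.2 once the event resolves | No more drug at this visit; premedicate and dose at the next scheduled visit |
| Apply the Grade 3 descriptor | 6.2 Grade 3 or 4, and 6.1.3 | Permanent discontinuation |

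No sentence chooses between the routes. The Grade 2 premedication advice is not limited to patients who completed the restarted infusion without recurrence, and 6.1.3 contains no exception for recurrence at reduced rate.

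**Time to re-exposure on the first route** (Section 5.1 and Section 5.2 Part B dosing tables)

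- Part A, weeks 1-12: Day 15 − Day 1 = 14 days.
- Part A, weeks 13-24: Day 22 − Day 1 = 21 days.
- Part A, weeks 25-96: Day 29 − Day 1 = 28 days.
- Part B combination phase: Day 22 − Day 1 = 21 days, and no less than 18 days under the text of that section.

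**Infusions at which the instruction could apply, per patient**

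- Part A: C1-C2, 2 × 3 = 6; C3-C4, 2 × 2 = 4; C5-C10, 6 × 3 = 18. Total 6 + 4 + 18 = 28.
- Part B: nivolumab 2 × 2 + 2 × 2 + 3 × 3 = 17; ipilimumab 2 × 2 = 4. Total 17 + 4 = 21.

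These totals are simply every scheduled infusion. They count opportunities and are not expected events. An expected number would need a rate of Grade 2 reactions and a rate of recurrence on restart. The documents give neither, so none is calculated.

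**The case against.** The strongest reply is that the controlling rules are already there. Reactions must be graded by CTCAE v4.03, the Grade 3 descriptor sits in the very next bullet with its permanent stop emphasised, and 6.1.3 is binding whereas the 6.2 advice is open to local modification. On this view the bullet tells bedside staff what to do at that moment, the premedication line serves the wider Grade 2 group, and 6.1.2 cannot override 6.1.3. All that is missing is a cross-reference.

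Part of this stands. A site that regrades correctly reaches the right action, and 6.1.3 does govern once the event is Grade 3. The bullet also never says in so many words that a patient with recurrence may be re-dosed. But these points show which rule should prevail without removing the contrary instruction. The recurrence step stops drug for one visit, and advice on later doses follows in the same bullet with no exception. Staff following it have no prompt to look elsewhere.

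A second reply is that the authors may have wanted to allow premedicated rechallenge after a mild recurrence at half rate. The documents do not exclude that as an intention. It would, however, require an exception in 6.1.3 and in the Grade 3 or 4 bullet, and neither contains one. The text needs correcting on either reading.

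**Conclusion.** The concern holds. The Grade 2 recurrence instruction is wrong as written, because following it leads to a further dose for a patient whom 6.1.3 requires to stop. It should be corrected at the next amendment.

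The consequence is serious for an affected patient, but few patients are likely to be affected. The problem arises only after a Grade 2 reaction, an interruption, resolution, a restart and a recurrence, and Section 6.2 itself regards such reactions as unlikely. Sample size, power and the primary analysis do not change.

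The conclusion rests on reading the items in the Grade 3 descriptor as alternatives, as their semicolons suggest, and on treating 6.1.3 as binding over the advisory text of 6.2. No event rate is assumed.

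**What to change.** In the Grade 2 bullet of Section 6.2, replace the recurrence sentence with wording to this effect:

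> If symptoms return after restart, stop the infusion, regrade the event as Grade 3 per CTCAE v4.03, manage it under the Grade 3 or 4 bullet, and permanently discontinue study treatment per 6.1.3.

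Then limit the premedication advice for later infusions to patients who had no recurrence after restart.

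The cost is one replaced sentence and one qualifying phrase at the next amendment, plus a memo to sites. There are no new procedures, visits or patients. Treatment ends only for patients whom 6.1.3 already requires to stop.

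If the sponsor does intend rechallenge after recurrence, the alternative is to state it as an explicit exception in both 6.1.3 and the Grade 3 or 4 bullet.

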6.3 Protocol Therapy Discontinuation

In addition to discontinuation from therapy related to toxicities as outlined above, a subject will also be discontinued from protocol therapy and followed per protocol under the following circumstances outlined below. The reason for discontinuation of protocol therapy will be documented on the electronic case report form (eCRF)

- Documented disease progression **NOTE:** Repeat scan should be performed in 4-6 weeks to confirm PD. A subject may be granted an exception to continue on treatment with confirmed radiographic progression if clinically stable or clinically improved. If PD confirmed patient can move to Part B and or go off study treatment.

- Completed 96 weeks of treatment with nivolumab (Part A) or 60 weeks of (nivolumab + ipilimumab for 12 weeks followed by nivolumab monotherapy for up to 48 weeks) (Part B). **NOTE:** 96 or 60 weeks of study medication are calculated from the date of first dose of each Part.
- Site investigator determines a change of therapy would be in the best interest of the subject
- Subject or legal representative (such as a parent or legal guardian) withdraws consent and requests to discontinue protocol therapy, whether due to unacceptable toxicity or for other reasons
 - In a subject decides to prematurely discontinue protocol therapy (“refuses treatment”), the subject should be asked if he or she may still be contacted for further scheduled study assessments. The outcome of that discussion should be documented in both the medical records and in the eCRF.
- Female subject becomes pregnant
- Unacceptable adverse experiences
- Intercurrent illness that prevents further administration of treatment
- Protocol therapy is interrupted for > 6 weeks (calculated from the date of the first missed dose). Any potential exceptions to this criterion must be discussed with and approved by the study chair.
- Noncompliance with protocol treatment or procedure requirements
- The subject is lost to follow-up
- Administrative reasons

6.2 Protocol Discontinuation

If a subject decides to discontinue from the protocol (and not just from protocol therapy) all efforts should be made to complete and report study assessments as thoroughly as possible. A complete final evaluation at the time of the subject's protocol withdrawal should be made with an explanation of why the subject is withdrawing from the protocol. If the reason for removal of a subject from the study is an adverse event, it will be recorded on the eCRF.

7. STUDY CALENDAR & EVALUATIONS

Study Evaluation	Screening	Part A (\pm 3 days)						Part B (\pm 3 days)						End of Treatment (EOT)	Follow Up ¹²			
		Induction		Maintenance				Prior to Part B	Induction		Maintenance							
		Cycle = 6 weeks			Cycle = 12 weeks				Cycle = 6 weeks		Cycle = 12 weeks							
		C1-C2		C3-C4		C5-C10			C1 ¹⁰ -C2		C3-C4		C5-C7					
		-28 days	-14 days	D 1	D 15/29	D 1	D 22	D 1	D 29/57	-28 days	D 1	D 22	D 1	D 22	D 1	D 30 100 \pm 14 days		
REQUIRED ASSESSMENTS																		
Informed Consent	X																	
Medical History/Smoking history	X																	
Diagnosis and Staging	X																	
Physical Exam ¹	X		X X	X X	X X	X X	X X	X	X X	X X	X X	X X	X X	X X				
Vital signs/ECOG PS Status ¹	X		X X	X X	X X	X X	X X	X	X X	X X	X X	X X	X X	X X				
AEs & concomitant medications	X		X X	X X	X X	X X	X X	X	X X	X X	X X	X X	X X	X X				
LABORATORY ASSESSMENTS																		
Complete Blood Cell Count with diff (CBC) ²	X	X	X X	X X	X X	X X	X X	X	X X	X X	X X	X X	X X	X X				
Comprehensive Metabolic Profile (CMP) ²	X	X	X X	X X	X X	X X	X X	X	X X	X X	X X	X X	X X	X X				
Amylase, Lipase, LDH, CPK ³	X		X		X		X	X	X X		X X		X X		X			
HBV, HCV ³	X																	
Thyroid Function (TSH) ³	X		X		X		X	X	X X		X X		X X		X			
Pregnancy test (serum or urine) ⁴			X					X										
DISEASE ASSESSMENT																		
CT of chest ⁵	X				X ⁵		X ⁵		X			X ⁵		X ⁵				
CT or MRI of abdomen and pelvis ⁵	X				X ⁵		X ⁵		X			X ⁵		X ⁵				
TREATMENT EXPOSURE																		
Nivolumab ⁶			X X	X X	X X	X X	X X	X	X X	X X	X X	X X	X X	X X				
Ipilimumab ⁶									X X									
SPECIMEN COLLECTION																		
Whole Blood for Somatic Testing ⁷			C1															
PBMCs and plasma ⁷			X ⁷		X ⁷		X ⁷		X ⁷									
Archival Tumor Tissue ⁸	X ⁸																	
Fresh Tissue ⁸		X ⁸							X ⁸									
SPECIMEN BANKING																		
Whole Blood, Plasma and Serum ⁹			C1											X				
FOLLOW UP																		
Survival Status, Therapy															X			

Key to Footnotes

1. If the screening physical exam is conducted within 24 hours of dosing on Day 1, then a single examination may count as both the screening and pre-dose evaluation. Vitals required are temperature, pulse, respiratory rate, blood pressure, and oxygen saturation.
2. Hematology Labs should include CBC with differential (hemoglobin, hematocrit, white blood cells, platelets, neutrophils, lymphocytes, eosinophils and monocytes). Additional draws must be incorporated when monitoring recovery from any hematologic AE. Chemistry Labs should include albumin, BUN, creatinine, ALT, AST, bilirubin serum alkaline phosphatase, glucose, total protein, sodium, potassium, chloride, HCO₃, calcium. Labs should be performed on the day of treatment but may be drawn up to 72 hours before to ensure return of results prior to dosing.
3. Other labs to be drawn: amylase, lipase, LDH, direct bilirubin (only if total bilirubin is elevated), uric acid and CPK Day 1 of every Cycle during treatment. Thyroid function will be monitored Day 1 of each cycle during treatment. TSH will be monitored and T3 and T4 (free versus total) should be drawn at site investigators discretion. It is suggested that if TSH is elevated T3 and T4 values may be done. At screening, testing should be performed for hepatitis C antibody and HBs Ag utilizing local standard informed consent procedures prior to this laboratory collection. These tests could be repeated later during the course of the study if clinically indicated.
4. Women of child-bearing potential must have a negative serum or urine pregnancy test within 24 hours prior to treatment with nivolumab and again at crossover to Part B for screening purposes.
5. Non-CNS Imaging should include a chest, abdomen and pelvis CT. Imaging of other sites should be obtained when clinically indicated. If follow up scans indicate partial or complete response, a repeat confirmatory scan should be obtained within 12 weeks (but no sooner than 6 weeks). Subjects with equivocal disease progression (e.g. a new lesion in the setting of major disease regression and the absence of or improvement in disease related symptoms) should have a scan confirming disease progression 4-6 weeks following the initial scan showing RECIST defined PD. Part A imaging will occur at baseline within 4 weeks of C1D1 of Part A, then at week 12 (after C1 and C2 of Part A Induction), week 18 (after C3 and before C4 of Part A Maintenance), week 24 (after C4 of Part A maintenance) and then every 12 weeks (\pm 1 week). Patients with symptomatic and radiographic PD will not require a confirmatory scan before proceeding to Part B of this study. Following crossover, imaging and calendar will be reset at Cycle 1. Part B imaging will occur at baseline within 4 weeks prior to crossover, then at week 12 (after C1 and C2 of Part B Induction), week 18 (after C3 and before C4 Part B Maintenance), week 24 (after C4 Part B Maintenance) and then every 12 weeks (\pm 1 week). Every 12 weeks radiology imaging will occur if the patient is < 2 years from study entry (or < 2 years from crossover), then radiology imaging will occur every 6 months (\pm 4 weeks) until 5 years from study entry. If tumor assessments are available for subjects who have not yet experienced progressive disease (PD) at the time treatment is discontinued, the follow-up tumor evaluations will be documented in the eCRF until PD or death is confirmed, or until another treatment is initiated.
6. 1 Cycle= (6 weeks) for Part A (induction and maintenance C3 and C4) and Part B (induction and maintenance C3 and C4). 1 Cycle = 12 weeks for Part A maintenance C 5-10 and Part B maintenance C5-C7. Treatment and follow-up schedule is the same for either nivolumab monotherapy or ipilimumab/nivolumab combination. Patients responding in Part A will receive treatment at most through Cycle 10 (week 96). Patients crossing over to Part B will receive treatment at most through Cycle 7 (week 60) from start of Part B. They will then have treatment stopped and be followed until disease progression or study closure. Once confirmed progression is confirmed or stable disease for 48 weeks (end of Cycle 6), nivolumab monotherapy will be discontinued for Part A and the patient will undergo evaluation for Part B treatment.
7. Mandatory Samples: Peripheral blood for somatic baseline testing will be collected prior to treatment on C1D1 Part A. PBMCs and plasma are preferred (or whole blood) for TCR assay and will be collected prior to treatment (C1D1), C3D1, C5D1 (Part A) and at time of progression (Prior to Part B). See Correlative Laboratory Manual (CLM) for additional details.

8. Archival tissue of a metastatic lesion obtained within 1 year prior to study registration (within 4 weeks preferred) and tumor tissue from nephrectomy is required if available. In addition to archival tissue of a metastatic lesion and nephrectomy, patients must have at least one site of disease (not including bone metastases) accessible for biopsy. If biopsy/resection of a new lesion or primary tumor and slow freezing of fresh tissue for single cell RNAseq study (as specified in the CLM) is not feasible, the subject is not eligible for the study. All biopsies must be core needle or excisional. Fine needle aspirate is not acceptable. NOTE: The tissue collected from a surgical resection or multiple core biopsies of either a metastatic lesion or primary tumor for the slow freezing of fresh tissue after the patient has signed consent for the study could also be used for collecting the FFPE specimens. See Correlative Laboratory Manual for complete details.
9. For Part A only: Whole blood will be collected prior to treatment C1D1. Whole blood for plasma and serum prior to treatment on C1D1 and at the D30 end of treatment visit. All samples will be banked for unspecified cancer related research (optional). See Correlative Laboratory Manual for complete details.
10. Patients on Part B should be contacted weekly during Cycles 1 and 2. If a patient reports symptoms at any time during these cycles or abnormal labs are noted at the regularly scheduled visits (C1 D22, C2 D1 or D22) then more frequent laboratory testing and clinic visits are encouraged.. This decision is at the discretion of the site investigator.
11. An End of Treatment (EOT) visit should occur 30 and 100 days (\pm 7 days) from last dose of study drug. For patients experiencing toxicities, additional visits may be necessary and may occur every 2 weeks (\pm 3 days) until toxicities resolve, are stable, or start of new systemic therapy. Depending upon the toxicity, the every 2-week assessment may be accomplished via phone call, email or other avenues as appropriate. Mode of assessment will be at site investigator's discretion. If patients have progressive disease as the reason for discontinuation from study, the D100 may be a phone call.
12. Follow up is for subjects that have discontinued study treatment. Subjects should be followed every 3 months if < 3 years from study registration and every 6 months if 3-5 years from study registration. Patients who develop disease progression on Part B or on Part A (if ineligible for Part B) will be followed for survival only. Follow up may be accomplished via clinic visit, phone call, or other avenues as appropriate. A window of \pm 14 days will be applied to follow up.

